#### **5.5.1.3 Sensitivity analysis of the primary estimand for the primary endpoint analysis, Frequentist approach**

For subjects who received rescue treatment or who have permanently discontinued IMP prior to the endpoint of interest, observed data after the IEs will be considered non-response. Any missing data for such subjects will be imputed as non-response.

Missing data at the endpoint of interest, for subjects who do not experience the IEs prior to that, will be handled as follows; For subjects in the delgocitinib cream 20 mg/g group and the cream vehicle group, missing data will be imputed from a Bernoulli distribution with parameter  $p$  value 0.1. The same parameter  $p$  will be used for both treatment groups. The parameter value 0.1 is based on the response rate of IGA-CHE TS at Week 16 in the cream vehicle group in the phase 2b trial in adults (LP0133-1273) and will introduce uncertainty due to missing data. A MI procedure (100 iterations) will be used.

For each of the 100 complete datasets, the risk difference will be based on a logistic regression model including treatment group and baseline IGA-CHE score as factors. The logistic regression model will be used to estimate the risk difference and associated 95% confidence interval based on the standardised estimator presented in Ge M et al. (2) and the variance estimator presented in Bartlett JW (3). The results of the analyses will be combined using Rubin's rule to provide the estimated treatment difference and associated standard error, and the 95% CI for the treatment difference will be calculated. In case of no missing data this analysis will not be performed.

#### **5.5.1.4 Supplementary analysis of the primary endpoint using the primary estimand along with historical and trial data, Frequentist approach**

Historical data used for this analysis is from trials LP0133-1401 and LP0133-1402. Missing data for subjects who do not experience an IE prior to the Week 16 visit will be imputed as non-response.

The risk difference between the 2 treatment groups will be based on a logistic regression model including treatment group, baseline IGA-CHE score, trial ID [i.e., trials LP0133-1401, LP0133-1402, and LP0133-1426] and interaction between treatment and trial ID as factors. Vehicle will be used as reference for treatment and LP0133-1426 as the reference for trial ID. The logistic regression model will be used to estimate the risk difference and associated 95% confidence interval will be estimated based on the delta method (<https://www.stata.com/support/faqs/statistics/delta-method/>).

Additionally, the estimate and 95% CI of interaction between treatment and trial ID for the logistic regression model, (including the factors: treatment group, baseline IGA-CHE score, trial ID and interaction between treatment and trial ID) will be presented.

#### **5.5.1.5 Additional analyses for the primary endpoint using the primary estimand and the sensitivity analysis of the primary estimand, Frequentist approach**

To be able to compare the results from LP0133-1426 with the analyses performed in LP0133-1401 and LP0133-1402 two additional analyses will be performed for the primary endpoint using the primary estimand.

In the primary endpoint additional analysis, missing data for subjects who do not experience an IE prior to Week 16 will be imputed as non-response (see Panel 8). The difference in response rates between the two treatment groups will be analysed using the CMH test stratified by baseline IGA-CHE score. The difference in response rates with 95% CI will be calculated by the Mantel-Haenszel method stratified by baseline IGA-CHE score.

THIS DOCUMENT CONTAINS CONFIDENTIAL INFORMATION AND MUST NOT BE COPIED OR MADE AVAILABLE TO ANY THIRD PARTY WITHOUT THE PRIOR WRITTEN CONSENT OF THE LEO PHARMA GROUP

In the sensitivity analysis of primary endpoint additional analysis, missing data for subjects who do not experience an IE prior to Week 16 will be imputed based on a Bernoulli distribution as described in section [5.5.1.3](#).

For each of the 100 complete datasets, the difference in response rates will be analysed by the Mantel-Haenszel method stratified by baseline IGA-CHE score. The results of the analyses will be combined using Rubin's rule to provide the estimated treatment difference and associated standard error, and the 95% CI for the treatment difference will be calculated.

#### **5.5.1.6 Binary endpoint analyses using the primary estimand, Frequentist approach**

The remaining binary endpoints will be analysed in a similar manner as the primary endpoint (that is including treatment group and baseline IGA-CHE score as factors), see section [5.5.1.2](#).

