### **14.3.8 Key secondary endpoint analysis, Frequentist approach**

The key secondary endpoints will be analysed in the same manner as described in Section 14.3.6 for the primary endpoint.

THIS DOCUMENT CONTAINS CONFIDENTIAL INFORMATION AND MUST NOT BE COPIED OR MADE AVAILABLE TO ANY THIRD PARTY WITHOUT THE PRIOR WRITTEN CONSENT OF THE LEO PHARMA GROUP

[Panel 18](#) provides an overview of which estimand (the composite strategy) and missing data strategy (non-responder imputation) is to be used in the analyses of the key secondary endpoints.

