Secondary objectives: To evaluate the health-related quality of life of twice-daily applications of delgocitinib cream 20 mg/g compared with cream vehicle in the treatment of adolescents with moderate to severe CHE.	Bayesian and Frequentist.	Primary.	Response achieved without IEs.	Initiation of rescue treatment, permanent discontinuation of IMP. Composite strategy.	Risk difference.	Key secondary endpoints: 
 
• Reduction of HESD itch score (weekly average) of <math>\geq 4</math> points from baseline at Week 16.
 
• Reduction of HESD pain score (weekly average) of <math>\geq 4</math> points from baseline at Week 16.
 
• Reduction of HESD score (weekly average) of <math>\geq 4</math> points from baseline at Week 16.
 

	Frequentist.	Primary.	Change from baseline to Week 16 without IEs.	Initiation of rescue treatment, permanent discontinuation of IMP. Composite strategy.	Difference in mean change.	Secondary endpoint: 
 
• Change in cDLQI score from baseline to Week 16.
 

1) Among subjects with a baseline HESD itch score (weekly average)  $\geq 4$  points.

2) Among subjects with a baseline HESD pain score (weekly average)  $\geq 4$  points.

3) Among subjects with a baseline HESD score (weekly average)  $\geq 4$  points.

**Abbreviations:** cDLQI = Children's Dermatology Life Quality Index; CHE = chronic hand eczema; HECSI = Hand Eczema Severity Index; HECSI-90 = at least 90% improvement in HECSI score from baseline; HESD = Hand Eczema Symptom Diary®; IE = intercurrent event; IGA-CHE = Investigator's Global Assessment for chronic hand eczema®; IGA-CHE TS = IGA-CHE treatment success, i.e. an IGA-CHE score of 0 (clear) or 1 (almost clear) with a  $\geq 2$ -step improvement from baseline; TS = treatment success.

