#### 5.5.1.1 Definition of binary endpoints

The primary endpoint for LP0133-1426 is the binary endpoint "IGA CHE TS at Week 16 (IGA CHE TS refers to a score of 0 [clear] or 1 [almost clear] with a  $\geq 2$  step improvement from baseline)".

The remaining binary endpoints (key secondary, secondary, and exploratory) are:

- HECSI 90 at Week 16.
- Reduction of HESD itch score (weekly average) of  $\geq 4$  points from baseline at Week 16 (Among subjects with a baseline HESD itch score (weekly average)  $\geq 4$  points.).
- Reduction of HESD pain score (weekly average) of  $\geq 4$  points from baseline at Week 16 (Among subjects with a baseline HESD pain score (weekly average)  $\geq 4$  points.).
- Reduction of HESD score (weekly average) of  $\geq 4$  points from baseline at Week 16 (Among subjects with a baseline HESD score (weekly average)  $\geq 4$  points.).
- IGA-CHE TS at Weeks 2, 4, 8, and 12.
- HECSI-90 at Weeks 4, 8 and 16.
- HECSI-75 at Weeks 4, 8, and 16.
- Reduction of HESD itch score (weekly average) of  $\geq 4$  points from baseline at Weeks 2, 4, 8 and 16 (Among subjects with a baseline HESD itch score (weekly average)  $\geq 4$  points.).
- Reduction of HESD itch score (weekly average) of  $\geq 3$  points from baseline at Weeks 2, 4, 8, and 16 (Among subjects with a baseline HESD itch score (weekly average)  $\geq 3$  points.).
- Reduction of HESD pain score (weekly average) of  $\geq 4$  points from baseline at Weeks 2, 4, 8 and 16 (Among subjects with a baseline HESD pain score (weekly average)  $\geq 4$  points.).
- Reduction of HESD pain score (weekly average) of  $\geq 3$  points from baseline at Weeks 2, 4, 8, and 16 (Among subjects with a baseline HESD pain score (weekly average)  $\geq 3$  points.).

THIS DOCUMENT CONTAINS CONFIDENTIAL INFORMATION AND MUST NOT BE COPIED OR MADE AVAILABLE TO ANY THIRD PARTY WITHOUT THE PRIOR WRITTEN CONSENT OF THE LEO PHARMA GROUP

- Reduction of HESD score (weekly average) of  $\geq 4$  points from baseline at Weeks 2, 4, 8 and 16 (Among subjects with a baseline HESD score (weekly average)  $\geq 4$  points).
- Reduction of HESD score (weekly average) of  $\geq 3$  points from baseline at Weeks 2, 4, 8, and 16 (Among subjects with a baseline HESD score (weekly average)  $\geq 3$  points.).

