#### **5.5.1.2 Primary endpoint analysis using the primary estimand, Frequentist approach**

The primary endpoint will be analysed as follows: Let the treatment effect be defined as the risk difference  $\mu$  = (delgocitinib cream 20 mg/g minus cream vehicle), then the hypothesis to be tested is:

- $H_0: \mu \leq 0$  against  $H_a: \mu > 0$ .

The hypothesis will be tested for delgocitinib cream 20 mg/g vs. cream vehicle based on the primary analysis for the primary estimand.

Missing data for subjects who do not attend the visit for the endpoint of interest and do not experience an IE prior to this visit will be imputed as non-response.

The risk difference between the 2 treatment groups will be based on a logistic regression model including treatment group and baseline IGA-CHE score as factors. The logistic regression model will be used to estimate the risk difference and associated 95% confidence interval based on the standardised estimator presented in Ge M et al. (2) and the variance estimator presented in Bartlett JW (3).

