#### **5.5.2.2 Analysis of continuous endpoints for the primary estimand**

For subjects who received rescue treatment or who have permanently discontinued IMP prior to the endpoint of interest, observed data after the IEs will be considered non-response by using WOCF (including the baseline value).

Missing data for subjects who do not experience an IE prior to the visit for the endpoint of interest will be imputed as WOCF (including the baseline value). Similarly, missing data at the endpoint of interest for subjects who do experience an IE prior to this visit will be imputed as WOCF (including the baseline value).

The change (or percentage change) from baseline to the endpoint of interest will be analysed using an ANCOVA model with effects of treatment group, baseline IGA-CHE score, and baseline value (endpoint of interest). LSMeans will be estimated using observed margins. The difference in the LSMeans between the treatment groups will be presented along with the corresponding 95% CI and nominal p-value.

THIS DOCUMENT CONTAINS CONFIDENTIAL INFORMATION AND MUST NOT BE COPIED OR MADE AVAILABLE TO ANY THIRD PARTY WITHOUT THE PRIOR WRITTEN CONSENT OF THE LEO PHARMA GROUP

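### The supportive frequentist models for the three HESD 4-point responder endpoints omit the baseline HESD score, which costs some precision and protection against chance imbalance but causes no bias

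*SAP*

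**What the plan says.** For the primary endpoint, SAP 5.5.1.2 specifies a "logistic regression model including treatment group and baseline IGA-CHE score as factors", with a standardised risk difference. SAP 5.5.1.6 carries this to the remaining binary endpoints, which are "analysed in a similar manner as the primary endpoint (that is including treatment group and baseline IGA-CHE score as factors". Protocol 14.3.8 agrees: "The key secondary endpoints will be analysed in the same manner as described in Section 14.3.6 for the primary endpoint". SAP Section 6, which lists changes from the protocol, adds no covariate.

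The three HESD key secondary endpoints are reductions of at least 4 points in the weekly average of itch, pain or total score at Week 16. Each is restricted to subjects whose own baseline is at least 4. For itch, SAP 5.5.1.1 puts it as "Among subjects with a baseline HESD itch score (weekly average") of 4 points or more, and SAP Panel 1 words the total score likewise: "Among subjects with a baseline HESD score (weekly average").

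For the continuous versions of the same scales, SAP 5.5.2.2 uses an "ANCOVA model with effects of treatment group, baseline IGA-CHE score, and baseline value (endpoint of interest"). Protocol 14.3.10 specifies the same ANCOVA. Neither document says why the responder models differ from it.

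**The concern.** For IGA-CHE treatment success, baseline IGA-CHE is both the stratification factor and the outcome's own baseline, so one covariate does both jobs. Carried over to HESD, the same covariate set keeps the stratification factor and loses the outcome's baseline. An investigator's grade of 3 or 4 is a weak stand-in for a patient-reported weekly average.

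For HESD the link between baseline and response is built into the endpoint. On a 0-10 scale, a subject who enters at 4.0 responds only by reaching 0, and a subject who enters at 9 responds at 5 or below. Restricting the analysis to baseline 4 or more still leaves baseline free to range from 4 to 10.

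What is at stake is the quality of a supportive estimate. The vehicle arm has at most 23 subjects, and the Bayesian analyses of these endpoints borrow an effective sample size of roughly 35 to 60 vehicle subjects (Protocol 14.3.17.3). Readers will look at the frequentist estimates beside those results, so it is worth making them as precise as the collected data allow.

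**Working it through.** **Inputs.** Arms of 69 and 23 (Protocol 14.3.17); one-sided 2.5% (SAP 5.1); adult average response rates from Protocol 14.3.17.3: itch 47.4% vs 21.1%, pain 49.6% vs 24.3%, total 45.5% vs 21.6%. Counting all 92 subjects is an upper bound, because only those with baseline 4 or more enter each analysis. The association between baseline HESD and response appears nowhere in the documents and is assumed below.

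**The plan's own figures.** The plan states no frequentist power for the HESD endpoints. Its nearest frequentist figure is at least 80% for the primary endpoint at 40.2% vs 10.5%. The pooled-variance formula gives 80.7%, so the arm sizes and level are read correctly. Its Bayesian power above 80% for the HESD endpoints also reproduces from the rounded SAP mixture priors: itch 92.8%, pain 88.6%, total 87.1%.

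**Step 1: itch without own-baseline adjustment.** Using an unpooled standard error:

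- Variance = 0.474 × 0.526/69 + 0.211 × 0.789/23 = 0.00361 + 0.00724 = 0.01085, so SE = 0.1042.
- Power = Φ(0.263/0.1042 − 1.96) = Φ(0.565) = 71.4%.
- The same formula gives 65.1% for pain and 62.7% for total.

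The pooled formula gives lower levels (62%, 57% and 53%). The comparison with and without the covariate matters here, not the level.

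**Step 2: variance with and without own baseline, IGA-CHE kept in both models.** Simulation of the standardised logistic risk difference for HESD total (45.5% vs 21.6%, 69:23, 3,000 trials per row). It assumes 30% of subjects with severe IGA-CHE and a correlation of 0.3 between baseline HESD and the latent scale behind that grade.

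| Assumed log-odds slope per baseline SD | Variance ratio, adjusted/current | Simulated power, current → adjusted |
|---|---|---|
| 0 | 1.01 | 61.6% → 61.2% |
| 0.3 | 1.00 | 62.4% → 63.4% |
| 0.6 | 0.96 | 61.0% → 63.1% |
| 1.0 | 0.86 | 63.1% → 69.2% |
| 1.5 | 0.77 | 61.5% → 73.8% |

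The mean risk difference was about 0.24 in both models in every row, and type I error agreed to within 0.2 percentage points. The simulated one-sided error was about 5-6% for both models, reflecting the small vehicle arm and the large-sample SE. The powers therefore compare the two models and are not absolute values.

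**Step 3: how strong the 4-point rule could make the association, for itch.** Baseline was taken as truncated normal on 4-10 (means 6-7, SD parameters 1.5-2.5). Reduction was baseline times a logit-normal fraction, calibrated to 47.4% and 21.1%. The implied correlation was 0.16-0.47 on active and 0.13-0.37 on vehicle. Adjusted power was 72.2% to 79.0% against 71.4%, a gain of 1 to 8 points. Simulating the estimator in three of these scenarios gave variance ratios of 0.87, 0.91 and 0.98. In the Step 1 formula, dividing by √0.98 and √0.87 gives 72% and 77%.

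**Step 4: chance imbalance.** The standard error of the between-arm difference in a baseline score is √(1/69 + 1/23) = 0.24 SD. If the SD is 1.4 points (assumed), that is 0.34 points. With a response slope of 0.05 to 0.17 per point (assumed), a one-SE imbalance moves the unadjusted risk difference by 0.34 × 0.05 = 1.7 to 0.34 × 0.17 = 5.7 percentage points.

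**Step 5: sparsity.** Expected vehicle responders if all 23 qualify: itch 23 × 0.211 = 4.9, pain 23 × 0.243 = 5.6, total 23 × 0.216 = 5.0. The chance of none is 0.789^23 = 0.4% for itch. For HECSI-90 the figures are 23 × 0.109 = 2.5 and 0.891^23 = 7%.

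**The case against.** The strongest case against is that nothing confirmatory depends on these models. Only the Bayesian analyses are in the testing hierarchy (SAP 2.1). They use responder counts per arm without covariates, so the change leaves them as they are. Imbalance under randomisation is already reflected in the confidence interval, and it will be visible because baseline values of the key secondary measures are tabulated (Protocol 14.3.2). IGA-CHE severity is the sole stratification factor and is described as strongly prognostic, so the present covariate set is defensible. All of this stands and limits the weight of the point.

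A reader might infer that these models are the only adolescent-only check on the borrowing from adults. The documents do not support that. SAP 5.5.1.9 re-runs the Bayesian analysis of the primary and all key secondary endpoints with the non-informative weight varied from 0 to 1, and weight 1 is an adolescent-only result. The baseline-adjusted ANCOVA also uses adolescent data alone on the same scales.

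A reader might also infer gains near 12 points by assuming a correlation of 0.5 (itch 71% to 83%). That value lies above the 0.13-0.47 range that the 4-point rule produced in Step 3. Even that range comes from a model in which reduction scales with baseline, which builds in part of the association.

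Finally, the argument might be stretched to HECSI-90. That endpoint is a relative threshold: "HECSI-90 = at least 90% improvement in HECSI score from baseline". The fixed-drop argument therefore does not apply, and the vehicle arm is sparser.

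What survives is the unexplained difference between the two model families, and the omission of a baseline value already collected for every subject in the HESD responder analyses.

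**Conclusion.** The point holds as a low-cost improvement to supportive analyses of the three HESD responder endpoints. The current models are valid: the omission gives no bias in the risk difference and no type I error inflation, and no confirmatory conclusion or sample-size figure changes. They are less precise than they could be and leave chance baseline imbalance uncorrected.

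The size rests on an association that the documents do not give. Adjustment would reduce variance by about 0-4% if the association is weak to moderate and about 14-23% if it is strong. For itch, modelling the 4-point rule directly gives roughly 1 to 8 power points. If there were no association, the cost would be about 1% in variance. These figures assume the adult response rates and all 92 subjects qualifying; fewer will qualify, which lowers power in both models.

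**What to change.** Before unblinding, amend SAP 5.5.1.6 so that the logistic models for the HESD itch, pain and total 4-point responder endpoints include treatment group, baseline IGA-CHE and the corresponding baseline HESD weekly average as a continuous covariate. Keep the standardised risk-difference estimator. Prespecify what happens under separation or with zero responders in an arm, for example a return to the current model or a penalised fit. Record the change in SAP Section 6 as a departure from Protocol 14.3.8. For HECSI-90, own-baseline adjustment should be at most an optional sensitivity analysis.

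The cost is one covariate in text and code. It needs no new data and adds no missing values, because a baseline score is required to enter each HESD responder analysis. The downside is one more parameter with about 5 expected vehicle responders at best. Fitting failed in at most 2 of 3,000 simulated trials, but that count does not capture separation: at 0.43%, about 13 of 3,000 itch trials would have no vehicle responder. The current model shares that problem, so the fallback is useful either way. If the sponsor prefers to keep the current model, one sentence explaining why it differs from the ANCOVA would remove the inconsistency.

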#### **5.5.1.7 Primary endpoint analysis using the primary estimand, Bayesian approach**

For the Bayesian analysis of the primary endpoint the estimand used is the primary estimand i.e., the composite strategy. The treatment effect (defined as proportion of responders for delgocitinib cream 20 mg/g minus the proportion of responders for cream vehicle) will be evaluated based on the calculated posterior distribution of the treatment difference.

Delgocitinib cream 20 mg/g is considered superior to cream vehicle if the 2.5% percentile of the posterior distribution of the treatment difference is  $\geq 0$ . Appendix [7.2.2](#) provides an example of R code to perform the Bayesian analyses.

The MAP approach using a hierarchical model for the between-study heterogeneity is used to derive the informative priors from historical data. The prior for the between-trial heterogeneity for the primary endpoint IGA-CHE TS, which controls the amount of borrowing from historical information, is set to  $\tau = 0.5$  and the prior weight on the non-informative part of the prior is set to 0.2 (20%).

The 'gMAP' function in the statistical package 'RBesT' in R is used for the calculations. The seed used for both vehicle and delgocitinib cream 20 mg/g is 1331426, the number of iterations is set to 50.000 and the warmup is set to 5000.

For IGA-CHE the historical response rates from LP0133-1401 and LP0133-1402 (see [Panel 9](#)) are used to calculate the informative MAP prior both for the cream vehicle as well as for the delgocitinib cream 20 mg/g.

**Panel 9: IGA-CHE responders from LP0133-1401 and LP0133-1402**

	LP0133-1401 a		LP0133-1402 b	
	Vehicle	Delgocitinib 20 mg/g	Vehicle	Delgocitinib 20 mg/g
Number of responders	16	64	11	91
Total number of subjects randomised	162	325	159	313

**Notes:** **a** = 1401 numbers are from final\_20230308, t\_20100\_igat\_byvis.txt. **b** = 1402 numbers are from final\_20230324, t\_20100\_igats\_byvis.txt.

After calculation of the MAP prior, the expectation maximization algorithm is used to approximate the parametric mixture density with the ‘automixfit’ function in the statistical package ‘RBest’.

Finally, the prior is robustified (to control the type-1 error) by adding a non-informative component to the MAP prior in case the historical data deviate from the adolescent data. The non-informative mixture component weight is set to 20% as previously mentioned.

The univariate beta mixture components of the map prior for vehicle and delgocitinib 20 mg/g calculated for IGA-CHE can be seen in a rounded version with 2 decimal points in [Panel 10](#) and [Panel 11](#). The actual numbers are used in the further calculations. The prior distributions shown in the SAP are fixed and will not change after un-blinding.

